6.2 Multiple testing and significance

Multiple testing of the co-primary endpoints will be handled by Bonferroni-adjustment (i.e. by multiplying p-values by two and presenting estimated treatment effects with 97.5% confidence intervals). Tests of treatment effect and effect modification by IFNGS will be carried out sequentially, so that effect modification will only be tested if a significant treatment effect is found. This is in accordance with the alpha set at p=0.05 in the original protocol without Bonferroni correction. The p-values from the secondary and exploratory analyses will be adjusted for multiple testing using the method of Benjamini and Hochberg³³, which control the false discovery rate (FDR). Adjustment will be carried out for secondary and exploratory end points separately and for tests of treatment effect and effect modification separately. In all analyses an adjusted p-value < 0.05 will be considered statistically significant.

6.3 Tools for statistical analysis

Analysis will be done in an updated version of Rstudio with an updated version of R⁴⁵. The LMMstar package⁴⁶ will be used for linear mixed model analyses. The code will be available on Github (<https://github.com/[name]/Lupex-Statistics>).

8 IMPLEMENTATION OF THE STASTITICAL ANALYSIS PLAN

Following approval of the statistical analysis plan by the writing committee it will be published at the Github account(<https://github.com/[name]/Lupex-Statistics/tree/main/Documents>), the clinicaltrials.gov website, and the Centre for Physical Activity website (www.aktisundhed.dk) prior to commencing statistical analysis.

10 EXPECTED OUTLINE OF REPORTS

The study report will be aimed at a publication in clinical journals, thus each report will contain 3500-4000 words and 4 to 6 main figures and tables depending on the journal.

The 2010 CONSORT guidelines⁴⁸ will be followed when reporting the data.

The primary endpoints (fatigue and aerobic capacity) and the secondary endpoints, along with relevant related exploratory endpoints such as diet, physical activity measured by accelerometers, body composition and adverse events will be published in one paper.

The cardiometabolic outcomes, such as results from the 82-Rb-Pet-CTs, the pulmonary function tests and the echocardiographic outcomes as a second paper. The direct intra-bout related changes from exercise, such as the cytokine measurements will make up a third paper.

11 OVERVIEW OF CONTENT IN REPORTS

Paper 1: Aerobic Capacity, Fatigue, IFN-signature, SF-36, Diet, OGTT, physical activity AX3, Body composition, Adverse events – Overuse pain & discomfort vs overuse injury.

Paper 2: 82-Rb-Rest/Stress-PET-CT, Echocardiography, Capillaroscopy, & Pulmonary Function testing.

Paper 3: Cytokine measurements doing acute exercise bout, Vagus™ measurements.

12 Paper 1 – Primary & Key Secondary outcomes

Working title: Adaptations in **aerobic capacity and fatigue** induced by 4x4 HIIT in systemic lupus erythematosus patients and the modulation by type 1 Interferon gene signature. – An outcome assessor blinded randomized controlled single-blinded clinical trial.

Outcomes reported in this paper:

Aerobic Capacity, Fatigue, IFN-signature, SF-36, Diet, physical activity AX3, Body composition, Adverse events.

12.1 Tables in paper

Table 1. Baseline characteristics separated by randomization group. Aerobic capacity, weight & waist circumference separated by screening/baseline.

Table 2. Changes from baseline and estimated treatment differences for the Primary and secondary outcomes, and related exploratory outcomes as suggested by the CONSORT statement.

Table 3. As table 2 but with randomization groups further divided according to percentiles of the IFN-score at baseline and the estimated treatment difference replaced by the estimate for de IFN-score*randomization group interaction.

12.2 Figures in paper

Figure 1. CONSORT flow diagram.

Figure 2. Trends in the primary outcome over time divided by percentiles of the IFN-score.

Figure 3. Trends in secondary and related exploratory outcomes over time.

12.3 Tables in supplement

eTable 1. Adherence to prescribed exercise.

eTable 2. Descriptive statistics of per protocol vs. protocol violators.

eTable 3. Self-reported diet, macronutrients and energy intake divided by intervention group.

eTable 4. Daily steps and METs in free-living conditions as reported by accelerometers.

eTable 5. Adverse reactions & events following randomization.

eTable 6. Other relevant characteristics measured at screening, baseline and followup, separated by intervention group at followup.

eTable 7. Baseline data grouped into the same percentiles of the IFN-score as table 3.

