#### 3.9.3 Acute Exercise Bout

At baseline and follow-up all patients, both control and intervention patients will perform an acute symptom-limited exercise bout on a bicycle ergometer (Monark LC4, Monark Exercise AB, Vansbro, Sweden) at CFAS. This exercise bout will be identical to the exercise interventions and consist of 10 minutes of warm up at 40-60% maximum heart rate (HRmax), followed by 4 sets of 4 minutes of high intensity interval training (HR>85%HRmax) these sets are followed by 4 sets of 3 minutes of medium intensity (40-60% HRmax), for a total of 28minutes, and finally a 0-7 min cool-down of 40-60% HRmax or below. This gives a total exercise of 38-45 minutes.

These acute exercise bouts are identical to the intervention and gives us an opportunity to study the changes in cytokine activity during exercise for patients with SLE following intervention.

[figure not shown]

Figure 4 Acute Exercise Bout, HRMax = Maximal Heart Rate

During and following this bout, the small package of blood samples will be drawn to assess for markers of inflammation, as described in 3.9.7.3, for a total of 10 times, as described in 3.8.4 (see Figure 4).

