##### 4.8.1 Safety evaluation

All adverse events (AEs) and serious adverse events (SAEs) observed by the investigators will be reported in the case report form (CRF) and to REC as requested, from the start of the trial (after written consent) to the final day of protocol procedure. An AE is defined as any untoward medical

occurrence in a participant, which does not necessarily have a causal relationship with the trial intervention. AEs are graded as the following:

Grade 1: The AE is noticeable to the subject but does not interfere with subject's every day's life activities; it may or may not require additional concomitant therapy.

Grade 2: The AE interferes with the subject's daily activities; it usually requires additional therapy.

Grade 3: The AE is intolerable and requires additional therapy.

Grade 4: The individual is at immediate risk of death at the time of the AE; it does not refer to an event which hypothetically might have caused death if it was more severe. Life-threatening events result in a SAE.

An SAE is any untoward medical occurrence or effect that at any dose results in death, is life-threatening, requires hospitalization or prolongation of existing hospitalization, results in persistent or significant disability or incapacity, or is a congenital anomaly or birth defect.

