#### 4.9 Procedure for recording and handling AEs and SAEs

Full description of these procedures is attached in Appendix A. All AEs/SAEs related to the study assessments (including the exercise intervention) will be recorded immediately and notified in the CRF. All AEs/SAEs (both those that are anticipated and unanticipated) will be recorded on adverse event forms and published with study results. We will also collect patients' self-report of AEs/SAEs, and report these in the CRF. These forms will include a description and classification of the event, date of onset, date resolved, whether the event was serious or not (ICH criteria), relationship of the event to the study (1=none, 2=unlikely, 3=possible, 4=probable, 5=definitely), action taken, and whether the study was suspended or not.

All SAEs, regardless of causation, will be reported to REC within one week (in any SAE resulted in death, an immediate report within 24 hours will be sent.) Once a year the sponsor will summarize all SAEs and report these to REC. If at any point it is considered medically unsafe by the principal investigator for a patient to continue in the study, the patient will be excluded from the study and offered appropriate support.

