Participants flow through the project with a screening visit, where aerobic capacity is assessed, a baseline visit with most of the outcomes, and a baseline-acute bout session consisting of one exercise bout and the measurements of the autonomic nerve system. A subgroup of patients will then undergo a 82-Rb-rest-stress-PET-CT evaluating cardiac adaptation. Patients are then randomized to exercise or control. Whereafter they will undergo a followup visit, another acute bout (termed the follow-up acute bout) and at last if they did one at baseline, they will do a repeat 82-Rb-rest-stress-PET-CT.

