13.3 Tables in supplement

eTable 1. Adverse reactions & events following randomization.

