14.3 Tables in supplement

eTable 1. Self-reported Diet

eTable 2. Adverse reactions & events following randomization.

eTable 3. Estimated marginal means of all the blood samples measured at all timepoints during the acute exercise bout.

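### The SAP plans no adverse event table or listing for the period from consent to randomisation, although Protocol 4.9 commits to publishing all events

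*SAP*

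**What the plan says.** **Recording.** Protocol 4.8.1 has AEs and SAEs entered in the case report form (CRF), and sent to the ethics committee as requested, "from the start of the trial (after written consent) to the final day of protocol procedure".

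**Publication.** Protocol 4.9 covers events related to study assessments as well as to the exercise programme, and states: "All AEs/SAEs (both those that are anticipated and unanticipated) will be recorded on adverse event forms and published with study results".

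**Order of events.** SAP 4 describes a screening visit with an aerobic test, a baseline visit, a baseline acute bout and a PET scan in a subgroup. Only after these does it say: "Patients are then randomized to exercise or control". Of the acute bouts, Protocol 3.9.3 says: "These acute exercise bouts are identical to the intervention".

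**Planned AE tables.** There is one in each paper:
- Paper 1, SAP 12.3: "eTable 5. Adverse reactions & events following randomization"
- Paper 2, SAP 13.3: "eTable 1. Adverse reactions & events following randomization"
- Paper 3, SAP 14.3: "eTable 2. Adverse reactions & events following randomization"

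SAP 10, 11 and 12 also name adverse events as content of paper 1, without giving a time window.

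**The concern.** The protocol promises to publish every recorded event, and recording starts at consent. The SAP's tables start later, at randomisation. The period between the two is not idle: it holds two tests to exhaustion, one full interval session, an adenosine stress scan in some participants and a biopsy in those who agree to one. For every participant, controls included, it also holds the first interval session of the study.

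At stake is how complete the published safety record is for the test battery and for first exposure to this form of exercise in SLE. An event at baseline that stopped someone from being randomised bears directly on tolerability, yet it would fall in none of the three tables. Papers 2 and 3 are the ones that report the PET scans and the acute bouts, and each would tabulate events only for the follow-up half of its own procedure.

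**Working it through.** The plan gives no figure to reproduce here. The check compares the two documents and then counts scheduled procedures.

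**1. Commitment against plan.** Protocol 4.9 sets what is to be published: all AEs and SAEs, with assessments in scope. The tables in SAP 12.3, 13.3 and 14.3 cover the period after randomisation. The other tables and figures listed in SAP 12 to 14 include none for events between consent and randomisation. The AE entries in SAP 10 to 12 set no window and define no further table.

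**2. What lies before randomisation.** The order of the VO2max test, baseline visit, acute bout and PET comes from SAP 4. Protocol 3.9.2 places VO2max tests straight after consent, on the first baseline day and at follow-up. Protocol Table 1 gives visits 1, 2 and 5 for VO2max, 4 and 7 for the acute bout, 3 and 6 for PET, and 2 and 5 for biopsy. SAP 4 does not mention biopsy, so its timing rests on Protocol Table 1.

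**3. Counts.** Inputs: 55 participants allocated 1:1 (SAP 4), a PET subset of 30 to 40 (SAP 5.3.8), and at least 40 completers, since recruitment stopped once 40 was reached (SAP 4). The final number of completers is not stated, so both ends of the range, 40 and 55, are shown. I assume that each participant did every scheduled baseline test.

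Share outside the tables = before / (before + after), where before = number randomised × procedures scheduled before randomisation, and after = number completing follow-up × procedures scheduled after it.

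| Procedure | All 55 complete | 40 complete |
|---|---|---|
| VO2max test (2 before, 1 after) | 110 / (110 + 55) = 110/165 = 67% | 110 / (110 + 40) = 110/150 = 73% |
| Acute bout (1 before, 1 after) | 55 / (55 + 55) = 55/110 = 50% | 55 / (55 + 40) = 55/95 = 58% |

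For PET, the share is 30/60 to 40/80 = 50% if everyone scanned at baseline returns. For biopsy, it is the first of each pair; the number opting in is not given.

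Two groups of procedures are not counted because the documents give no numbers: the repeat test with stress ECG that Protocol 3.9.2 provides for some participants, and anything done in people who consented but were never randomised.

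**4. What the extra period adds in precision.** With zero events in n procedures, the one-sided 95% upper bound on the risk per procedure is 1 − 0.05^(1/n).
- VO2max: n = 55 gives 5.3%; n = 165 gives 1.8%.
- PET at the upper subset size: n = 40 gives 7.2%; n = 80 gives 3.7%.

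These bounds treat repeated procedures in one person as independent, so they only illustrate the scale.

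**5. What is covered.** The programme schedules 12 × 3 = 36 sessions per exerciser. All follow randomisation, as do the follow-up tests, bouts, scans and biopsies.

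**The case against.** Several objections have force.

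- **A by-arm table should start at randomisation.** This is right. Earlier events cannot be attributed to an arm and would dilute the comparison. The tables are sound as planned; the gap is that nothing accompanies them.
- **The captions belong to an outline of reports and withdraw nothing from the protocol.** SAP 10 to 12 mention adverse events without a window, so baseline events could still be given in text or in another supplement item. This stands in part. But the same limit appears in all three papers, and no item is assigned to the earlier period.
- **Protocol 4.8.1 governs recording, not publication.** Correct. A table that starts at randomisation does not contradict it. The shortfall is against 4.9 alone.
- **The full AE procedure is in Appendix A, which is not among the documents.** True, but 4.9 itself states the publication commitment.

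A reader might infer that baseline events go unreported, or that someone who has an event at baseline and is never randomised vanishes from the record. The documents do not support this. Events are recorded in the CRF. All SAEs go to the ethics committee whatever their cause, and are summarised yearly (Protocol 4.9). The SAP plans a CONSORT flow diagram (12.2) and a participant flow figure (12.4), where losses before randomisation can appear. Protocol 4.10 plans a public data repository. A flow diagram, however, gives counts and reasons; it is not an AE record by procedure.

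A reader might also infer that the safety evidence on the training programme rests on a selected group of survivors. That goes too far, since every supervised session is covered. What is missing is one acute bout and the baseline tests per participant.

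**Conclusion.** The point holds as a gap between the protocol's commitment to publish all AEs and SAEs and the tables that the SAP plans. Events between consent and randomisation are recorded, but no publication has a planned table or listing for them.

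Per participant, the gap covers 2 of 3 scheduled VO2max tests, 1 of 2 acute bouts, 1 of 2 PET scans in the subset and the first optional biopsy. Across 55 participants it covers 67% to 73% of VO2max tests and 50% to 58% of acute bouts, as completers range from 55 down to 40. These are shares of procedures, not of events; the documents give no event counts.

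The conclusion rests on the visit order in SAP 4 and Protocol Table 1, since the protocol text names no randomisation visit. Severity is minor to moderate. It is a matter of safety reporting: no estimate, test or analysis set is affected.

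**What to change.** Keep the three by-arm tables of events after randomisation. Add to SAP 12.3 one pooled descriptive table or listing of AEs and SAEs from consent to randomisation, in all consented participants, including those never randomised. It should identify the related procedure (VO2max test, acute bout, PET, biopsy, blood sampling) and any event that led to non-randomisation. Cross-refer to it from SAP 13.3 and 14.3, so that the PET and acute-bout papers account for both halves of their procedures.

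The cost is a few lines of SAP wording and one extra descriptive table. Protocol 4.8.1 already requires the data to be collected, and no hypothesis test changes. The layout is open; Protocol 4.9 requires only that the events be published.

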12.4 Figures in supplement

eFigure 1. Flow of participants.

eFigure 2. Volcano plots depicting change in gene counts from baseline to followup in both intervention groups.

eFigure 2a Intervention group changes in genes

eFigure 2b Control group changes in genes

eFigure 2c Between group differences in gene count changes.

eFigure 3. Overview of the intervention.

eFigure 4. Overview of the OGTT, levels of Insulin, Glucose and C-peptide at different timepoints separated by intervention and IFN-percentiles.

eFigure 5. False discovery rate of exploratory endpoints – Histogram of p-values.

13 Paper 2 – Cardiopulmonary outcomes

Working title: Adaptations in **cardiopulmonary functions** induced by 12 weeks of 4x4 HIIT in systemic lupus erythematosus patients and the modulation by type 1 Interferon gene signature on exercise. – A secondary analysis of an outcome assessor blinded randomized controlled clinical trial.

Outcomes reported in this paper: 82-Rb-Rest/Stress-PET-CT, Echocardiography, Capillaroscopy, & Pulmonary Function testing.

13.1 Tables in paper

Table 1. Baseline characteristics, including the

Table 2. Changes in 82-Rb-Rest/Stress-PET-CT, Echocardiography and Lung Function findings, separated by intervention group.

Table 3. As table 2 but further separated into low/mid/high IFN groups.

13.2 Figures in paper

Figure 1. CONSORT flow diagram.

Figure 2. Trends in outcomes over time divided by percentiles of the IFN-score.

13.3 Tables in supplement

eTable 1. Adverse reactions & events following randomization.

13.4 Figures in supplement

eFigure 1. False discovery rate – Histogram of p-values in this paper.

14 Paper 3 – Intra-bout cytokine response and resting vagal tone outcomes

Working title: Adaptations in **resting vagal tone and intra-bout cytokine response to singular exercise bout** induced by 12 weeks of 4x4 HIIT in systemic lupus erythematosus patients and the modulation by type 1 Interferon gene signature. – A tertiary analysis of an outcome assessor blinded randomized controlled clinical trial.

Outcomes in this paper: Acute Bout – Cytokine levels during exercise, sensitivity adjusted by hematocrit.

Vagus™ measurements

14.1 Tables in paper

Table 1. Baseline characteristics, separated by intervention group.

Table 2. Caloric and macronutrient intake, physical activity measured in steps/calories burned and METs in the randomization groups at follow-up.

Table 3. Estimated marginal means of blood sample concentration with 95%CI from the 9 timepoints in the acute exercise bout.

14.2 Figures in paper

Figure 1. CONSORT flow diagram.

Figure 2. Trends in outcomes over time divided by percentiles of the IFN-score.

14.3 Tables in supplement

eTable 1. Self-reported Diet

eTable 2. Adverse reactions & events following randomization.

eTable 3. Estimated marginal means of all the blood samples measured at all timepoints during the acute exercise bout.

14.4 Figures in supplement

eFigure 1.

Figure detailing the acute exercise bout.

eFigure 2.

Outcomes from the Vagus™ measurements at the specific timepoints

- Resting heart rate
- Rise from supine heart rate variability (HRV)
- Expiratory/inspiratory HRV

eFigure 3.

False discovery rate – Histogram of p-values in this paper.

16 UNFORMATTED TABLES WITH INTENDED CONTENT

Table 1 Baseline characteristics

	Control	Exercise	Total
Age (years)			
Sex (N (%)) female)			
SLE duration (years)			
SLE activity markers			
SLEDAI			
SLICC			
B2MG			
LYMPHOCYTES			
THROMBOCYTES			
Antibodies			
Anti-Sm			
ANTI-DsDNA			
NEITHER ANTI-DsDNA or ANTI-sm			

Table 2 – Change scores without IFN-difference

Outcome	Change from 0 to 12 weeks Mean \pm SD		Estimated treatment difference (95% CI, p-Value)
	Control (n=xx)	Exercise (n=yy)	
VO2max			
FSS			
SF-36 Aggregate Physical Component			
SF-36 Aggregate Mental Component			
Etc.			

Table 3 – Change scores with IFN quantiles							
Outcome	Change from 0 to 12 weeks Mean \pm SD						Estimated IFN:Treatment interaction (95% CI, p-Value)
	Control (n=xx)			Exercise (n=yy)			
	IFN-low	IFN-Mid	IFN-High	IFN-Low	IFN-Mid	IFN-High	
VO2max							
FSS							
SF-36 Aggregate Physical Component							
SF-36 Aggregate Mental Component							
Etc.							

IFN-Low = Lower 33% percentile of the IFN-scores, IFN-Mid 33%-66% percentile of the IFN-scores, IFN-High 67%-100% of IFN-scores.

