### **3.9.18 Data analysis**

At least 10 participants in each intervention group and 10 participants in each control group, will be included to obtain a significance level of 0.05 with a power of 80% to observe an increase in VO2max of 1.14ml/kg/min with a SD of 2.15 in the control group and an increase in VO2max of 3.80ml/kg/min with a SD of 3.34 in the intervention group based on a previous publication. If we assume a drop-out rate of less than 30% with 15 participants in each group, we will have at least a power of 80% even with 30% drop-out. With 14 participants in each group, we will achieve a power of 90%.

Similar results were gained when examining the study by Boström et al. were the control group had an increase in VO2max of 1.7ml/kg/min with an SD of 1.3 and the intervention group had an increase of 3.2ml/kg/min with an SD of 1.2. A significance of 0.05 and a power of 80% requires 12 subjects in each group.

Since we hope to be able to part our groups into patients with higher IFNGS being the patients with M3.4 and M5.12 and we assume one third of our patients will be in this group, including 30 patients for intervention will give us 10 “high IFNGS intervention” patients in total for this power calculation.

Results will be analysed according to a pre-defined statistical analysis plan and initial modelling of the primary outcome will be based on Analysis of Covariance (ANCOVA) performed with change (post-measure minus pre-measure) as the dependent outcome, with a fixed factor for group (two levels) and applying the value at baseline as a covariate.

$$k = \frac{n_2}{n_1} = 1$$

$$n_1 = \frac{(\sigma_1^2 + \sigma_2^2/K)(z_{1-\alpha/2} + z_{1-\beta})^2}{\Delta^2}$$

$$n_1 = \frac{(2.15^2 + 2.15^2/1)(1.96 + 0.84)^2}{2.66^2}$$

$$n_1 = 10$$

$$n_2 = K * n_1 = 10$$

$\Delta = |\mu_2 - \mu_1|$  = absolute difference between two means  
 $\sigma_1, \sigma_2$  = variance of mean #1 and #2  
 $n_1$  = sample size for group #1  
 $n_2$  = sample size for group #2  
 $\alpha$  = probability of type I error (usually 0.05)  
 $\beta$  = probability of type II error (usually 0.2)  
 $z$  = critical Z value for a given  $\alpha$  or  $\beta$   
 $k$  = ratio of sample size for group #2 to group #1

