3 HYPOTHESES

3.1 Primary Hypotheses

We hypothesize that 12 weeks of HIIT exercise will increase aerobic capacity and decrease fatigue score compared to no intervention, and further that the effects are modulated by IFNGS, more specifically:

1.

- a. HIIT is superior to no intervention control at improving aerobic capacity.
- b. The effect of HIIT on aerobic capacity is modulated by IFNGS, such that a higher IFNGS results in lower benefits of HIIT.

2.

- a. HIIT is superior to no intervention control at alleviating fatigue.
- b. The effect of HIIT on fatigue is modulated by IFNGS, such that a higher IFNGS results in less decrease of initial fatigue from HIIT.

Type 1 interferon induced changes to exercise adaptations in systemic lupus erythematosus patients.

Superiority is claimed if the difference is statistically significant and favors the HIIT intervention. In order to control the family-wise error rate, hypotheses 1 and 2 will be tested in parallel with Bonferroni-adjustment and hypotheses a and b will be tested hierarchically, so that hypothesis b is only tested if a is significant.

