4 TRIAL DESIGN, DATA COLLECTION AND OUTCOMES ASSESSMENT

The study protocol, detailing the hypotheses, methods, recruitment and conduct of the study has been published in a non-peer reviewed openly accessible preprint database³⁵. In brief, the study is a randomized control trial, consisting of 2 arms, labeled exercise and control. As outlined in the publicly available protocol³⁵; initial sample size calculations were based on a t-test for changes in VO₂max. Assuming a between group difference in aerobic capacity change scores similar to the 1989 Robb-Nicholson study³⁶ (mean: 2.66, 95%CI [0.36, 4.96]); resulted in 10 completers needed in each group, if we assumed a median split of IFN-score we would require 40 completers for four groups (low IFN control, Low IFN exercise, High IFN control and high IFN exercise). We assumed as much as a 30% dropout; which required a sample size of 60 participants. After reaching 40 completers, recruitment ceased, and only further participants already enrolled for baseline examination were included, this resulted in 55 participants included in the study. These were then stratified for sex and randomly allocated 1:1 to exercise or control. At www.clinicaltrials.gov the study is identified by NCT05478018. Prior to commencement the scientific ethics committee of the capital region of Denmark approved to trial with identifier H-21039032. The trial primarily took place at Centre for Physical Activity on Rigshospitalet, [name]. Recruitment took place primarily at the center for vasculitis and spine diseases on Rigshospitalet in [name]. 82-Rb-Pet-CT scans were conducted at the department of clinical physiology at Rigshospitalet, [name].

[figure not shown]

Figure 1 - Graphical hypothesis

The exercise group underwent 12 weeks of thrice weekly 45 minute HIIT exercise sessions, with 4 intervals of 4 minutes of high intensity exercise, defined as a heart rate above 85% of the maximal heart rate interspersed with 3 minute active breaks of pedaling against light resistance (less than 20% wattmax).

As noted above the hypotheses were that these 12 weeks would improve aerobic capacity and fatigue in SLE patients, and that it would improve more in patients with lower IFNGS.

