6 STUDY POPULATION, ANALYSIS SET AND STATISTICAL PRINCIPLES

Eligibility criteria have been previously published³⁵. In brief, the participants suffered from systemic lupus erythematosus, and fulfilled 10 or more points on the 2017 ACR/EULAR SLICC⁴³, were not pregnant, did not suffer from diabetes mellitus and were 18 years or older, both males and females were included.

As stated earlier, sample size calculation required 40 completers, the study included 55 participants.

Randomization was done in a 1:1 ratio, stratified on sex.

The statistical analyses will be carried out primarily in the modified intention to treat (mITT) population, excluding the participants who were randomized but were found ineligible as per the ineligibility criteria within the first week of randomization, while retaining the data from all other study participants as randomized regardless of compliance and study completion. Supplementary per protocol (PP) analyses will exclude data from participants in the exercise group who failed to show up for 80% or more of the exercise sessions (29 or more sessions needed attendance to be considered in the PP group).

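### SAP Table 2 heads the VO2max and FSS treatment effects with 95% confidence intervals, where SAP 6.2 requires 97.5%

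*SAP*

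**What the plan says.** SAP 6.2 sets the presentation of the co-primary results: the Bonferroni adjustment is made "by multiplying p-values by two and presenting estimated treatment effects with 97.5% confidence intervals". The same section gives the decision rule: "In all analyses an adjusted p-value < 0.05 will be considered statistically significant". SAP 3.1 confirms the structure: "hypotheses 1 and 2 will be tested in parallel with Bonferroni-adjustment and hypotheses a and b will be tested hierarchically".

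SAP 12.1 assigns the primary results to Table 2 of the first paper: "Changes from baseline and estimated treatment differences for the Primary and secondary outcomes", together with related exploratory outcomes. The shell of that table is in SAP 16. VO2max and FSS are its first two rows, followed by the SF-36 aggregate scores and further outcomes. One heading covers the last column for all of them: "Estimated treatment difference (95% CI, p-Value)". There is no footnote, split heading or exception for the co-primary rows, and no other part of the SAP reconciles the two levels.

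**The concern.** The same two estimates cannot be printed in that column at both 97.5% and 95%. These are the intervals for the trial's two primary results. Under 6.2 the interval and the adjusted p-value always agree, because a 97.5% interval excludes zero exactly when the doubled p-value is below 0.05. A 95% interval loses that agreement when the raw p-value lies between 0.025 and 0.05. Table 2 would then show an interval that excludes zero for an endpoint that the plan calls non-significant. The treatment-effect result also decides whether effect modification by the interferon signature is tested, so a reader going by the interval could think that step had been reached when it had not.

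**Working it through.** **1. The level in 6.2.** Two endpoints share a two-sided 0.05, so each gets 0.05/2 = 0.025, and the matching interval level is 1 − 0.025 = 97.5%. SAP 6.2 is internally correct. The shell's 95% does not match it.

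**2. Where interval and decision part.** A 95% interval excludes zero when the raw p < 0.05. The plan's rule needs 2p < 0.05, that is p < 0.025. Example: a raw p of 0.03 doubles to 0.06, which is not significant; the 95% interval excludes zero and the 97.5% interval includes it.

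**3. Difference in width.** Ratio of critical values:
- normal: 2.2414/1.9600 = 1.144
- t with 38 df: 2.3337/2.0244 = 1.153

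The 97.5% interval is therefore about 14% to 15% wider.

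**4. Inputs for the chance of a visible conflict on VO2max.**
- Difference 2.66 ml/kg/min: SAP 4, and 3.80 − 1.14 in Protocol 3.9.18.
- SDs: 2.15 in both arms, as in the Protocol's formula, or 2.15 and 3.34, from the Protocol's text ("3.80ml/kg/min with a SD of 3.34 in the intervention group").
- Completers: SAP 6 says "sample size calculation required 40 completers, the study included 55 participants". I assume 20 per arm (40/2) and 27 per arm (55/2 = 27.5, rounded down).
- Method: a two-sample t comparison with 2n − 2 df, as an approximation to the planned constrained mixed model.

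SE = sqrt((SD₁² + SD₂²)/n) and δ = 2.66/SE. The chance is P(t₀.₉₇₅ < |T| < t₀.₉₈₇₅), with T noncentral t with noncentrality δ.

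| n per arm (assumed) | SDs | SE | δ | Chance |
|---|---|---|---|---|
| 20 | 2.15, 2.15 | 0.680 | 3.91 | 3.0% |
| 20 | 2.15, 3.34 | 0.888 | 2.99 | 8.8% |
| 27 | 2.15, 2.15 | 0.585 | 4.55 | 0.8% |
| 27 | 2.15, 3.34 | 0.764 | 3.48 | 5.1% |

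**5. Range over all true effects.** Under no effect the chance is 0.05 − 0.025 = 2.5%. The maximum over δ, with 38 df, is about 12% (11.9%). This range serves for FSS too, because the sample size calculation covers VO2max only and gives no planning difference or SD for FSS.

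**6. Which VO2max results would be affected.** With 20 per arm the half-widths at 95% and 97.5% are:
- SD 2.15 in both arms: 2.0244 × 0.680 = 1.38 and 2.3337 × 0.680 = 1.59
- SDs 2.15 and 3.34: 2.0244 × 0.888 = 1.80 and 2.3337 × 0.888 = 2.07

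An observed difference between 1.38 and 1.59 ml/kg/min, or between 1.80 and 2.07, would show the conflict.

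**The case against.** The strongest reply is that this is clerical. Section 16 holds unformatted shells with open-ended rows, one generic heading spans primary, secondary and exploratory outcomes, and 6.2 is the specific rule for exactly these two estimates. An analyst who reads 6.2 knows what to compute. If the doubled p-value is printed as 6.2 requires, it also stands in the same cell as the interval and warns the reader. Much of this is fair: it limits the harm and explains why the correction is small. It does not remove the contradiction. The section's own title says the shells show intended content, and a shell is what gets filled in.

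Four stronger readings are tempting, and the documents do not support them.
- A reader might infer that the p-value column is wrong as well. The heading does not say whether the p-value is raw or adjusted, and 6.2 already requires doubling. It is unlabelled, not in conflict.
- A reader might infer that the family-wise error rises, to as much as 1 − 0.95² = 9.75% for two independent endpoints. That would need significance to be judged from the 95% intervals; 6.2 judges it from the adjusted p-value.
- A reader might count the 95% heading of Table 3 as a second error. SAP 6.2 sets 97.5% for estimated treatment effects and gives no level for the interaction, so that heading conflicts with nothing.
- A reader might extend the argument to the other rows of Table 2. Their p-values are Benjamini-Hochberg adjusted and can also disagree with a 95% interval, but 6.2 sets no other level for them, so 95% there contradicts nothing.

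**Conclusion.** The contradiction is real and confined to the confidence level for the VO2max and FSS rows of Table 2: 95% in the shell, 97.5% in 6.2. As the shell stands, the stated intervals for the two primary results do not follow the plan's own rule. Nothing in the hypothesis tests, the decision rule or the error control has to change.

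The practical size is modest. Per endpoint, the chance of an interval that excludes zero beside a doubled p-value above 0.05 is 2.5% under no effect and at most about 12% for any true effect. At the planned VO2max difference it is about 3% to 9% with 20 completers per arm and about 1% to 5% with 27. The planned-effect figures rest on assumed completer numbers, the Protocol's SDs and a two-sample approximation to the mixed model. The contradiction itself rests on the text alone.

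**What to change.** In the Table 2 shell, by header or footnote, give the VO2max and FSS rows 97.5% confidence intervals as 6.2 requires, and note that their p-values are Bonferroni-adjusted (doubled). Leave the other rows at 95%.

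The cost is one line in the shell. The visible downside is that the two primary intervals print wider by the 14% to 15% shown above; for VO2max with an assumed 20 per arm, that adds about 0.21 (1.59 − 1.38) to 0.27 (2.07 − 1.80) ml/kg/min to each half-width. No analysis, test or sample size changes.
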